**4.2****Scientific Rationale for Study Design**

The treatment burden of MS is significant and further evidence for the long-term effect of new therapies is needed (Derfuss 2020; Lucchetta 2020). This extension study of the CLARIFY MS trial will contribute to the knowledge on the long-term effect and safety of cladribine tablets for the third and fourth year after initiation of treatment, focusing on cognition and HRQoL, among adults with highly-active RMS.

Cladribine tablets treatment has a maximum duration of 20 days in 2 years, after which participants are to be monitored according to the SmPC for an additional 2 years (treatment-free). The design of this extension study is based on this cladribine tablet treatment-free monitoring period, with the participants visiting Investigators as part of routine clinical practice; most assessments are part of routine clinical practice, CCI [REDACTED]

The primary objective of this study is to assess cognition in participants with highly-active RMS at 4 years after initial dose of cladribine tablets. Participants with highly-active RMS are at high risk for early cognitive impairment. The prevalence of cognitive impairment in MS is reported to be around 43% to 70%. Cognitive impairment has a detrimental effect on the lives of MS patients by reducing social activities, increasing physical dependence, retarding progress in rehabilitation, and affecting everyday life activities (Langdon 2010).

To assess cognitive function over the study period, an expert consensus committee of neurologists and neuropsychologists, with extensive research and clinical experience of MS cognition, have recommended CCI [REDACTED].

The CCI [REDACTED] is a universally accepted assessment for cognitive function in MS that takes a short time to administer, is highly sensitive and reliable, and healthcare professionals can easily be trained to administer it, whereas qualified neuropsychologists are required for other similar assessments (Benedict 2012). The CCI [REDACTED]; a CCI [REDACTED] component has been correlated to CCI [REDACTED] (Batista 2012). The CCI [REDACTED] is collected routinely in MS care in all participating countries, while the other components of CCI [REDACTED] are not, as they have not been validated yet in some of the participating countries (including Austria, the Netherlands, and Denmark).

The secondary objective of this study is to assess HRQoL in participants with highly-active RMS at 4 years after initial dose of cladribine tablets. The HRQoL of patients with MS is lower than patients with any other chronic conditions, including ischemic heart disease, Type-2 diabetes, and Crohn's disease (Orme 2007). The Multiple Sclerosis Quality of Life 54 Questionnaire (MSQoL-54) is an ideal questionnaire to assess HRQoL in MS patients over a period of time, because it can address the impact of the low burden of treatment of cladribine tablets in overall HRQoL, which covers multiple domains, including role limitations, bodily pain, physical function, emotional wellbeing, energy, health perceptions, social function, cognitive function, health distress, sexual function, change in health, and overall quality of life.

Furthermore, an important CCI

In addition, while the efficacy of cladribine tablets on relapses and disease progression and safety have been demonstrated in previous clinical studies, evidence of efficacy and safety at the third and fourth year in patients with highly-active RMS in a real-world setting (cladribine tablets administration as per SmPC) is relatively limited. CCI are included as they play an important role in the management and monitoring of patients with MS (Oreja-Guevara 2015) and have provided important outcomes in previous cladribine tablets clinical studies.

Moreover, CCI may impact a participant's response to therapy, susceptibility to, and severity and progression of disease. Variable response to therapy may be due to CCI determinants that could impact cladribine tablet absorption, distribution, metabolism and excretion; mechanism of action of cladribine tablets; disease etiology; and/or molecular subtype of the disease being treated. CCI

The current pandemic due to the coronavirus disease 2019 (COVID-19), attributable to severe acute respiratory syndrome coronavirus 2 (SARS-CoV-2), has a major impact on clinical care and patients' lives (Stojanov 2020). Consequently, there may also be an impact on the study endpoints, in particular on HRQoL. To account for the potential impact of this pandemic, participants will be asked to fill out a COVID-19 Survey (Section 8.1.3).

#### 4.3 Justification for Dose

Not applicable.

#### 4.4 End of Study Definition

A participant has completed the study if he/she has completed all study parts, including the last scheduled procedure in the End of Study Visit (M48), as presented in the Schedule of Activities (Section 1.3). After the study completion, the participants' care will continue according to routine clinical practice.

The End of the Study is defined as the date of the last participant's Last Visit, globally.

### 5 Study Population

The criteria in Sections 5.1 and 5.2 are designed to enroll only participants, who are appropriate for the study; thereby, ensuring the study fulfills its objectives. All relevant medical and nonmedical conditions are considered when deciding whether a participant is suitable for this study.

---

Prospective approval of protocol deviations to inclusion and exclusion criteria, also known as protocol waivers or exemptions, is not permitted.

Before performing any study assessments that are not part of the participant's routine medical care, the Investigator will confirm that the participant or the participant's legal representative has provided written informed consent, as indicated in [Appendix 2](#).

## 5.1 Inclusion Criteria

Participants are eligible to be included in the study only if all the following criteria apply:

1. Participants having participated in the CLARIFY MS trial, who
  - a. Have at least CLARIFY MS Baseline data on SDMT
  - b. Received at least a single dose of cladribine tablets in the CLARIFY MS trial
  - c. Completed the Final Study Visit (M24) of the CLARIFY MS trial.
2. Capable of giving signed informed consent, as indicated in [Appendix 2](#), which includes compliance with the requirements and restrictions listed in the informed consent form (ICF) and this protocol.

## 5.2 Exclusion Criteria

Participants are excluded from the study if any of the following criteria apply:

1. Participant is considered by the Investigator and Sponsor, for any reason, to be an unsuitable candidate for the study.

### Prior/Concurrent Clinical Study Experience

2. Participation in other studies/trials.

## 5.3 Lifestyle Considerations

Not applicable.

## 5.4 Screen Failures

Individuals who do not meet the criteria for participation in this study (screen failure) may not be rescreened.

## 6 Study Intervention(s)

Not applicable.

### 6.1 Study Intervention(s) Administration

Not applicable.

---

**6.2 Study Intervention(s) Preparation, Handling, Storage, and Accountability**

Not applicable.

**6.3 Measures to Minimize Bias: Study Intervention Assignment and Blinding**

Not applicable.

**6.4 Study Intervention Compliance**

Not applicable.

**6.5 Concomitant Therapy**

Record in the case report form (CRF) all concomitant therapies (e.g., medicines or nondrug interventions) used from the time the participant signs the informed consent until completion of the study, including any changes. For prescription and over-the-counter medicines, vaccines, vitamins, and herbal supplements, record the name, reason for use, dates administered, and dosing information. In addition, the following concomitant therapies will be recorded in the CRF as well:

- Concomitant therapies that are linked to a serious adverse event (SAE), which were initiated during the CLARIFY MS trial, and are ongoing at the time of enrolling (i.e., signing the informed consent) in the extension study.
- Concomitant therapies that were initiated after the Final Study Visit of the CLARIFY MS trial (M24) and prior to enrolling (i.e., signing the informed consent) in the extension study.

Contact the Medical Monitor for any questions on concomitant or prior therapy.

There are no restrictions regarding concomitant therapies that a participant can be on during the study period; participants will be treated at the discretion of the Investigator.

- Disease-related: All concomitant medications used for conditions / symptoms related to MS (for example, pain, fatigue or weakness, incoordination, bladder dysfunction, spasticity).
- Medical history related: All concomitant medications used for a medical condition already reported in the participant's medical history (for example, any form of pain, especially lower back pain and headache, depression etc.) or family history (primary headache, insomnia etc.).
- Self-medication: As this is an outpatient study, special care will be taken to question participants on any self-medication, and they will be asked to respond about the details of the administration of the doses and the concomitant medications in a diary. The use of any herbal or natural products, or other "home remedies" is allowed. However, the use of these products, and the use of vitamins, nutritional supplements and all the other concomitant medicinal products should also be noted in a diary.

- Relapse management: In case of neurological events related to MS, with relapse criteria (Section 8.1.7.1), treatment will be at the discretion of the Investigator, following local good medical practice and international guidelines.
- Disease reactivation: In the case of disease reactivation, further disease-modifying treatment will be at the discretion of the Investigator.
- Prohibited medicines: As per SmPC for cladribine tablets.

## 6.6 Dose Selection and Modification

Not applicable.

## 6.7 Study Intervention after the End of the Study

Not applicable.

# 7 Discontinuation of Study Intervention and Participant Discontinuation/Withdrawal

## 7.1 Discontinuation of Study Intervention

Not applicable.

## 7.2 Participant Discontinuation/Withdrawal from the Study

- A participant may withdraw from the study at any time, at his/her own request or may be withdrawn at any time at the discretion of the Investigator for safety, behavioral, compliance, or administrative reasons.
- A participant will be withdrawn from the study if the participant enrolls in another study.
- At the time of discontinuing from the study, if possible, a Discontinuation Visit will be conducted, as listed in the Schedule of Activities (Section 1.3). The Schedule of Activities specifies the data to collect at study discontinuation and follow-up, and any additional evaluations that need to be completed. If a physical visit is not possible, an option for a telephone call is provided, to obtain reason for discontinuation and the safety assessment at least.
- If the participant withdraws consent for future involvement in the study, any data collected up to that point may still be used, but no future data can be generated, and any biological samples collected will be destroyed, unless the Investigator obtains permission to retain and evaluate the samples.
- A participant has the right at any time to request destruction of any biological samples taken. The Investigator will document this in the site study records.
- Participants who are discontinued/withdrawn from the study will not be replaced.

- The Investigator will secure the safety of the study participants and make every attempt to collect data.

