**Table 1 Objectives and Endpoints**

Objectives	Endpoints
Primary	
To assess cognitive impairment in participants with highly-active relapsing multiple sclerosis (RMS), having participated to the CLARIFY MS trial, at 4 years after initial dose of cladribine tablets	Percentage of participants with no or minimal decline in cognitive function, defined as an improved or stable Symbol Digit Modalities Test (SDMT) score or a decline of 4 points or less in the SDMT score, at 4 years after initial dose of cladribine tablets (M48) compared to SDMT score prior to initial dose of cladribine tablets (CLARIFY MS trial Baseline)
Secondary	
To assess health related quality of life (HRQoL) in participants with highly-active RMS, having participated in the CLARIFY MS trial, at 4 years after initial dose of cladribine tablets	
 
Change in HRQoL as measured by the Multiple Sclerosis Quality of Life-54 Questionnaire (MSQoL-54) physical and mental health scores at 4 years after initial dose of cladribine tablets (M48) compared to prior to initial dose of cladribine tablets (CLARIFY MS trial Baseline)
 
Change in HRQoL as measured by MSQoL-54 physical and mental health scores at 4 years after initial dose of cladribine tablets (M48) compared to M24
 

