**MS700568\_0158**

---

HRQoL=Health related quality of life; SDMT=Symbol Digit Modalities Test; MSQoL-54=Multiple Sclerosis Quality of Life 54 Questionnaire; RMS=Relapsing Multiple Sclerosis.

**Overall Design:** This is the extension study to the 2-year CLARIFY MS trial to observe participants during the third and fourth year after the initial cladribine tablet dose; no cladribine tablets will be administered during the extension study period. At the extension study Baseline, data will be collected retrospectively from the potential transition gap period between the CLARIFY MS trial and CLARIFY MS Extension study (i.e., between M24 and extension study Baseline). In addition, participants will attend visits for assessments at the extension study Baseline (planned to coincide with or be as near to M24 as possible to minimize the transition gap period), M36 at 36 months/3 years after initial dose of cladribine tablets, and M48 at 48 months/4 years after initial dose of cladribine tablets.

**Disclosure Statement:** This will be an open label, single arm, exploratory, multicenter, retrospective and prospective, 2-year Phase IV study. The purpose of the study is the evaluation of the effect of a treatment for highly-active RMS.

**Number of Arms:** 1

**Blinding:** Not applicable

**Number of Participants:** Depending on the drop-out rate of the parent study, it is expected that up to a maximum of 380 participants will be enrolled into the extension study. Assuming a drop-out rate over the course of the extension study of 10% to 20%, it is expected to achieve a maximum of 300 to 340 evaluable participants for the extension study.

**Study Intervention Groups and Duration:** The extension study will cover a 2-year period in which the participants will not be treated with cladribine tablets, which were administered in the CLARIFY MS trial.

[figure not shown]

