**Table 3** **Study Objectives**

Objectives	Endpoints
Primary	
To assess cognitive impairment in participants with highly-active RMS, having participated in the CLARIFY MS trial, at 4 years after initial dose of cladribine tablets	Percentage of participants with no or minimal decline in cognitive function, defined as an improved or stable Symbol Digit Modalities Test (SDMT) score a or a decline of 4 points or less in the SDMT score, at 4 years after initial dose of cladribine tablets (M48) compared to SDMT score prior to initial dose of cladribine tablets (CLARIFY MS Baseline)
Secondary	
To assess health related quality of life (HRQoL) in participants with highly-active RMS, having participated in the CLARIFY MS trial, at 4 years after initial dose of cladribine tablets	
 
Change in HRQoL as measured by Multiple Sclerosis Quality of Life 54 Questionnaire (MSQoL-54) physical and mental health scores at 4 years after initial dose of cladribine tablets (M48) compared to prior to initial dose of cladribine tablets (CLARIFY MS Baseline)
 
Change in HRQoL as measured by MSQoL-54 physical and mental health scores at 4 years after initial dose of cladribine tablets (M48) compared to M24
 

CCI	
To assess the long-term (4 years) safety and tolerability of cladribine tablets	
 
Occurrences of adverse events (AEs) and serious adverse events (SAEs) during the third and fourth year after initial dose of cladribine tablets
 

CCI	

Objectives	Endpoints
CCI	

Objectives	Endpoints
CCI	

Objectives	Endpoints

CCI
 
CCI [REDACTED] CCI
 
Visuospatial Memory Test-Revised; CVLT-II=California Verbal Learning Test-II; CCI [REDACTED]; HRQoL=Health related quality of life; CCI [REDACTED] MS=Multiple Sclerosis; MSQoL-54=Multiple Sclerosis Quality of Life 54 Questionnaire; CCI [REDACTED] RMS=Relapsing Multiple Sclerosis; SAE=Serious adverse event; CCI [REDACTED]; CCI [REDACTED]
 
CCI
	

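### Section 7.2 lets the Investigator end follow-up for compliance or behavioral reasons, which may selectively lose the Month 48 SDMT of participants whose cognition has declined

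*Protocol*

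**What the plan says.** Section 7.2 provides that a participant "may be withdrawn at any time at the discretion of the Investigator for safety, behavioral, compliance, or administrative reasons". Participants who leave are not replaced. A Discontinuation Visit is held where possible; failing that, a telephone call must obtain at least the reason and a safety assessment. The section closes with a general duty on the Investigator to try to collect data, but it does not say that a withdrawn participant is still due for M48.

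The Synopsis (Section 1.1) states that "no cladribine tablets will be administered during the extension study period". Section 7.1, "Discontinuation of Study Intervention", reads "Not applicable". The only thing a participant can discontinue here is follow-up.

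The primary endpoint (Tables 1 and 3) is the "Percentage of participants with no or minimal decline in cognitive function, defined as an improved or stable Symbol Digit Modalities Test (SDMT) score" or a fall of at most 4 points, at M48 against the CLARIFY MS Baseline. Table 6 describes this single-arm percentage with a Wilson 95% interval. Multiple imputation under different missingness assumptions is a sensitivity analysis.

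On numbers, the Synopsis says "it is expected that up to a maximum of 380 participants will be enrolled into the extension study", with 10% to 20% drop-out and at most 300 to 340 evaluable.

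**The concern.** In a treatment trial, withdrawing a participant for poor compliance can at least serve to stop a drug. Here it serves only to stop measurement, and measurement is the purpose of the study.

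What participants must comply with depends partly on memory and organisation: a continuous diary (Section 8.1.10), monthly questionnaires completed at home (Section 8.1) and yearly visits within 28 days of the due date (Section 4.1). Section 4.2 itself says that this population is at high risk of early cognitive impairment and that impairment affects daily life. Failing at these tasks is therefore a plausible sign of the decline that the primary endpoint counts as failure. Section 7.2 lets the Investigator end follow-up on that sign, although the participant still consents.

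If that happened, the missing M48 scores would be related to the outcome. With one arm there is no comparison in which such a loss could cancel. In an observed-case analysis it would raise the reported percentage directly.

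**Working it through.** **Inputs from the protocol.** Maximum enrolled N = 380; drop-out d = 10% to 20%; stated evaluable 300 to 340 (all Section 1.1).

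**Inputs assumed, because the protocol gives none.** Observed success p = 80%; share f of the missing who were withdrawn by Investigator decision = 25% to 50%; success q among them = 40%. Other missing participants are taken to have the observed success percentage. The primary percentage is taken as observed-case.

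**Step 1: the plan's own figure.** Evaluable = N × (1 − d). 380 × 0.90 = 342 and 380 × 0.80 = 304, which agree with the stated 340 and 300 after rounding. Lost: 380 × 0.10 = 38 and 380 × 0.20 = 76.

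**Step 2: upward bias.** With k = f × d × N participants withdrawn by the Investigator, the percentage in all 380 is [p(N − k) + qk] / N. The bias is p minus this, that is k(p − q) / N = f × d × (p − q).

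| Drop-out | Share Investigator-decided | k | Bias at 80% against 40% |
|---|---|---|---|
| 10% | 25% | 9.5 | 1.0 point |
| 10% | 50% | 19 | 2.0 points |
| 20% | 25% | 19 | 2.0 points |
| 20% | 50% | 38 | 4.0 points |

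**Step 3: how far the assumptions drive this.** Letting f run from 10% to 50% and q from 20% to 60%, still at 80% observed, the bias is 0.2 to 3.0 points at 10% drop-out and 0.4 to 6.0 points at 20%. Letting p also run from 70% to 90%, the ranges are 0.1 to 3.5 and 0.2 to 7.0 points.

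**Step 4: comparison with the sampling error.** At about 80% observed, the Wilson 95% interval is 75.6% to 84.0% for 274/342 (half-width 4.2 points) and 75.1% to 84.1% for 243/304 (half-width 4.5 points). The 1 to 4 points of Step 2 lie within the half-width. Only the more extreme combinations in Step 3 exceed it, such as 6.0 points at 20% drop-out with f = 50% and q = 20%.

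**Step 5: dependence on the missing-data rule.** If every missing M48 score counted as failure, the same data would give 274/380 = 72.1% and 243/380 = 63.9%. The upward bias would then be gone.

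**The case against.** Several points on the other side are sound.

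- A reader might infer that Section 6.4, by marking compliance "Not applicable", contradicts Section 7.2. It does not. Section 6.4 concerns compliance with the study drug. Section 8 separately requires adherence to the study design, so compliance in Section 7.2 has a clear meaning.
- A reader might infer that a missed visit leads straight to withdrawal. Section 7.3 requires the site to make contact, reschedule and counsel, and to make repeated attempts before declaring loss to follow-up. It does, however, also ask whether the participant should continue, which leaves the discretion of Section 7.2 in place.
- A reader might infer that withdrawn participants leave the denominator. The protocol does not say so. The Full Analysis Set is all eligible participants, the handling of a missing M48 SDMT is not stated in the visible text, and the Integrated Analysis Plan is not at hand. The word evaluable and the placing of imputation among the sensitivity analyses point towards an observed-case percentage, but that is an inference.
- MSQoL-54 is collected at the Early Discontinuation Visit. The cognition row of the schedule is redacted, so it cannot be said that SDMT is omitted there. Even if it is taken, it is not an M48 value.
- The study is more than diaries and questionnaires: Section 2.3 lists MRI scans and blood draws and calls the study interventional. Some Investigator discretion is therefore reasonable, and a site needs a ground for disruptive conduct.
- The clause is permissive, and nothing in the protocol suggests that it would be used against participants with cognitive decline. Section 9.4 attributes the expected missing data to loss to follow-up.

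These points limit the size and certainty of the concern. They do not answer its core: the clause lets follow-up end on a sign related to the outcome while the participant still consents, and the safeguards do not restore the M48 score.

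**Conclusion.** The point holds as a weakness of the protocol text, not as a demonstrated bias. Section 7.2 permits withdrawals that serve no treatment purpose and may selectively lose the M48 SDMT of participants whose decline shows as poor adherence.

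The only size that rests on the plan's figures is the 38 to 76 participants expected to be lost from 380. How many of these would be Investigator-decided is unknown. The 1 to 4 points of upward bias are illustrative. They require that a quarter to a half of the losses be Investigator-decided, that success be 40% in that group against 80%, and that the primary percentage be observed-case. The documents do not support the stronger conclusion that the reported percentage will be inflated.

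The change is worth making because it is cheap and prevents a loss that analysis cannot repair.

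**What to change.** In Section 7.2:

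1. Remove compliance as a ground for Investigator withdrawal.
2. Limit the behavioral ground to conduct that makes further visits unworkable, or unsafe for staff or others.
3. State, in line with the rescheduling steps of Section 7.3, that missed visits or incomplete diaries or questionnaires do not end follow-up, and that a participant who has not withdrawn consent remains due for the M48 SDMT and MSQoL-54.

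The safety and administrative grounds stay, as does the participant's own right to leave. The third change is needed because, without it, the same participants could still be withdrawn on administrative grounds.

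The cost is a short text change at the next amendment, with no new visit or procedure. The downside is that sites keep scheduling M48 for some participants who are hard to follow, and not all of them will attend, so the number of scores saved cannot be promised. A sensitivity scenario that counts Investigator-withdrawn participants without an M48 SDMT as failures is optional: Table 6 already provides for different missingness assumptions, and the detail belongs in the analysis plan.
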